4.2 Subgroups

The primary and secondary endpoints of the M-DBTP will be analyzed in the following subgroups:

- Number of prior treatment failures (1, 2, and 3 or more treatment failures)
- Medication overuse status at baseline (yes vs. no)

Selected exploratory endpoints of the E-DBTP for the first qualifying triptan-treated attack may be analyzed by medication overuse status at month 3 (yes vs. no) (see Section 9.5.3).

The subgroups will be re-examined for appropriateness and may be re-categorized (due to small sample size, for example, if there are < 10% of subjects within a subgroup) before unblinding.

5. Definitions

5.1 Definition of Terms Included in Study Endpoints

5.1.1 Efficacy Endpoints Based on Daily Diary Data Collection During M-DBTP

During the 4-week baseline period and the 12-week M-DBTP, headache start and stop date/time, pain feature/symptoms, acute headache medication and aura related information will be reported on a daily basis via optional any-time diar(ies) (available 24 hours) and mandatory evening diary (only available once daily from 17:00 to 23:59).

Acute Headache Medication (AHM)

Acute headache medications collected in the eDiary are classified separately as follows:

	Medication Group A
Acute headache medication (AHM)	Ergotamine-Based Migraine Medications
	Triptan-Based Migraine Medications
	Gepant-Based Migraine Medications
	Ditan-Based Migraine Medications

Non-Opioid Acute Headache Medications
Non-Opioid Butalbital Containing Medications
Opioid-Containing Acute Headache Medications
Opioid-Containing Butalbital Containing Medications

	Medication Group B
	Ergots
	Triptans
	Gepants
Acute headache medication	Ditans
(AHM)	Opiate or opioid-containing medication
	Opioid Combination-analgesic
	Non-opioid Combination-analgesic
	Simple analgesics/NSAIDs

Acute Migraine-specific Medication (AMSM)

A subset of acute headache medication consisting of triptan-based migraine medications and ergotamine-based migraine medications

Medication Overuse (MO)

Monthly acute headache medication days meeting at least one of the following criteria based on medication category B:

- \geq 10 days of triptans
- \geq 10 days of ergotamines
- ≥ 10 days of opiates or opioid-containing medications or opioid combination-analgesics
- \geq 10 days of non-opioid combination-analgesics
- ≥ 15 days of simple analgesics/NSAIDs if no other acute headache medications were used
- ≥ 10 days of a combination of triptans, ergotamines, opiates or opioid-containing meds or opioid combination-analgesic, non-opioid combination-analgesic medications or simple analgesics/NSAIDs whilst not satisfying medication overuse criteria in any of the individual medication categories alone

Number of Diary Days in a Monthly Interval	Monthly Days with Medication Use
• ≥ 14 days	Prorate to 28-day equivalent without rounding Number of observed days with medication use*28/number of (diary days or medication days) within each monthly interval
• < 14 days	Set to missing

Qualified Headache

A qualified headache is defined as

- A headache of duration \geq 30 minutes, or
- A headache with acute headache medications (migraine-specific or not) taken during the headache (start time and end time inclusive) with any length of duration, or
- An aura during which an acute migraine-specific medication is administered

Headache Day

A calendar day (00:00 to 23:59) in which the subject experiences \geq 1 qualified headache

Qualified Migraine Headache

A qualified migraine headache should meet at least one of the following criteria:

- A headache of duration ≥ 30 minutes, and meeting ≥ 1 of the following criteria (a and/or b):
 - a) \geq 2 of the following pain features:
 - Unilateral
 - Throbbing
 - Moderate to severe (based on the 3-level categorical pain severity)
 - Exacerbated with exercise/physical activity
 - b) \geq 1 of the following associated symptoms:
 - Nausea
 - Vomiting
 - Photophobia and phonophobia
- A headache during which an acute migraine-specific medication is administered regardless of the headache duration, pain features, and associated symptoms
- An aura during which an acute migraine-specific medication is administered

Migraine Day

A calendar day (00:00 to 23:59) in which the subject experiences \geq 1 qualified migraine headache

Migraine-free Day

A calendar day (00:00 to 23:59) **of a diary day** in which the subject does not experience any headache and aura, photophobia, phonophobia, and nausea/vomiting, **and does**

not take any acute headache medication

Diary Day

A calendar day (00:00 to 23:59) with complete headache, aura, and acute headache medication data recorded **via daily evening diary**

Information Day

A calendar day (00:00 to 23:59) which is either a headache day or a diary day

Migraine Attack in M-DBTP

A migraine attack is an episode of any qualified migraine headache. The following rules will be used to distinguish an attack of long duration from 2 attacks, or to distinguish between attacks and relapses:

- A migraine attack that is interrupted by sleep, or temporarily remits, and then recurs within 48 hours (recurrence time headache start time ≤ 48 hours) will be counted as 1 attack
- An attack treated successfully with medication but with relapse within 48 hours (recurrence time headache start time ≤ 48 hours) will be counted as 1 attack

Triptan-treated Migraine Attack in M-DBTP

A migraine attack with triptan taken during the attack (start time and end time inclusive)

Headache Pain Intensity (evaluated by NRS) in M-DBTP

Worst or peak pain intensity collected on a headache ranges from 0 to 10 with a higher score indicating more severe pain.

Pain intensity is reported when the headache end time is reported or in an evening diary on a daily basis for an ongoing headache. Therefore, there can be multiple pain intensity values reported for a headache that lasts for multiple days. In some circumstances, a headache which starts and ends on the same day may also have up to 2 pain intensity values reported when the headache ends after evening diary completion: 1) pain intensity is reported in the evening diary for the period between headache start time and diary completion time; 2) pain intensity is reported either in any-time diary or the next day's evening diary for the period between previous diary completion time and headache end time. The NRS headache pain intensity will be used to assess the monthly average peak pain intensity.

Headache Pain Intensity (3-level)

Worst or peak pain intensity collected on a headache in 3 levels (mild, moderate or severe) followed by the NRS pain intensity question when the preceding NRS headache pain intensity is reported to be \geq 4, worst or peak pain intensity (3 levels) is set as mild if NRS headache pain intensity is reported to be <4.

Duration of Headache With at Least Moderate Pain Intensity

Duration of headache with at least moderate pain intensity (in hours and minutes) will be collected only when "Moderate" or "Severe" intensity is reported based on the 3-level headache pain intensity scale.

Monthly Migraine Days (MMD)

Number of migraine days during one monthly interval as defined below.

Number of Diary Days in a Monthly Interval	Monthly Migraine Days
• ≥14 days	Prorate to 28-day equivalent without rounding Number of observed migraine days*28/number of (diary days or migraine days) within each monthly interval
• < 14 days	Set to missing

Monthly Headache Days (MHD)

Number of headache days during one monthly interval as defined below.

Number of Diary Days in a Monthly Interval	Monthly Headache Days
● ≥ 14 days	Prorate to 28-day equivalent without rounding
	Number of observed headache days*28/number of information days
	Note: An information day is either a headache day or a diary day.
• < 14 days	Set to missing

Monthly Hours of at Least Moderate Headache Pain Intensity

Number of Diary Days in a Monthly Interval	Monthly Hours of at Least Moderate Headache Pain Intensity
• ≥ 14 days	Prorate to 28-day equivalent without rounding Sum of hours of headaches with at least moderate pain intensity *28/number of (diary days or days with headache pain intensity) within each monthly interval
• < 14 days	Set to missing

Monthly Hours of at Least Moderate Headache Pain Intensity of Qualifying Oral Triptan Treated Migraine Attacks

Number of Diary Days in a Monthly Interval	Monthly Hours of at Least Moderate Headache Pain Intensity of Qualifying Oral Triptan Treated Migraine Attacks
• ≥14 days	Prorate to 28-day equivalent without rounding Sum of hours of at least moderate pain intensity of qualifying oral triptan treated migraine attacks *28/number of (diary days or migraine days) within each monthly interval
• < 14 days	Set to missing

Monthly Average Duration of at Least Moderate Pain Intensity in Migraine Attacks

Number of Diary Days in a Monthly Interval	Monthly Average Duration of at Least Moderate Pain Intensity in Migraine Attacks
• ≥14 days	Sum of all the reported duration with at least moderate headache pain intensity within an attack divided by number of attacks in each month If there is no migraine during the monthly interval, then the monthly average duration will be set to 0.
• < 14 days	Set to missing

Monthly Average Duration of at Least Moderate Pain Intensity in Qualifying Oral Triptan Treated Migraine Attacks

Number of Diary Days in a Monthly Interval	Monthly Average Duration of at Least Moderate Pain Intensity in Qualifying Oral Triptan Treated Migraine Attacks	
• ≥ 14 days	Sum of all the reported duration with at least moderate headache pain intensity within a qualifying oral triptan-treated attack divided by number of qualifying oral triptan-treated attacks in each month;	
	If there is no migraine during the monthly interval, then the monthly average duration will be set to 0.	
• < 14 days	Set to missing	

Monthly Average Peak Migraine Pain Intensity

Number of Diary Days in a Monthly Interval	Monthly Average Peak Migraine Pain Intensity
• ≥14 days	Sum of observed highest pain intensity scores (NRS) per migraine day divided by total number of migraine days with at least one measure of NRS; If there is no migraine day with NRS during the monthly interval, then the monthly average peak migraine pain intensity will be set to 0.
● <14 days	Set to missing

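### The average-attack-duration secondary divides by all attacks, so a headache attack with no recorded severity or duration is scored as 0 hours

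*SAP*

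**What the plan says.** SAP 5.1.1 gives the monthly rule for months with at least 14 diary days: "Sum of all the reported duration with at least moderate headache pain intensity within an attack divided by number of attacks in each month". The value is 0 if there is no migraine in the month and missing if there are fewer than 14 diary days. The exploratory average for qualifying oral-triptan-treated attacks follows the same form.

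Four other statements in SAP 5.1.1 decide what enters that ratio:

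- **Attack.** "A migraine attack is an episode of any qualified migraine headache".
- **Qualification by drug intake.** One sufficient criterion is "A headache during which an acute migraine-specific medication is administered regardless of the headache duration, pain features, and associated symptoms". An aura treated with such a drug also qualifies.
- **Severity.** "Pain intensity is reported when the headache end time is reported or in an evening diary on a daily basis for an ongoing headache".
- **Duration.** Hours of at least moderate pain "will be collected only when 'Moderate' or 'Severe' intensity is reported based on the 3-level headache pain intensity scale".

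The neighbouring endpoints have different denominators. The primary prorates by "number of (diary days or days with headache pain intensity) within each monthly interval". Peak pain divides by "total number of migraine days with at least one measure of NRS", but is set to 0 if no migraine day in the month has an NRS value.

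SAP 8.3 sends missing daily-diary data back to 5.1.1 and adds no rule at attack level. SAP 9.5.1 states that the primary and secondary endpoints have no sensitivity analyses.

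**The concern.** The denominator includes attacks for which the numerator was never observed. A patient may log a headache and a triptan, and then neither close the headache nor complete an evening diary while it is open. That headache still qualifies as migraine, but it has no rating and so no hours. It enters the average at 0 h, exactly as a mild-only attack does. The mild attack is a true zero; the unrated one is a missing value. An attack rated moderate or severe but lacking a duration gets the same score.

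The SAP anticipates missing ratings elsewhere: the peak-pain denominator is limited to days that have one. Triptan intake is also common by design, because inclusion criterion 107 asks for patients who typically start with an oral triptan on more than half of their at least moderate attacks.

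The endpoint is under type 1 error control and is planned at 81% power. If recording of attacks differed between arms, part of that difference would appear as a difference in pain duration, and no planned analysis would show it.

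**Working it through.** **1. The plan's own figure.** Inputs from SAP Table 3-1: effect -2.0 h, SD 8, two-sided 0.05, 288 per group less 10%, or 288 × 0.9 ≈ 259.

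- SE = 8 × √(2/259) = 0.703 h
- Power = Φ(2.0/0.703 − 1.96) = Φ(0.885) = 81.2%

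The stated 81% reproduces. The point concerns the definition, not the power statement.

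**2. One month, three rules.** Assume four triptan-treated attacks: three recorded at 8 h each, and one on a non-diary day with no rating.

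- SAP rule for average duration: 24/4 = 6.0 h.
- Evaluable attacks only: 24/3 = 8.0 h.
- Primary, with 24 diary days: 24 × 28/24 = 28.0 h. The unrated day drops out; had it counted, the result would be 24 × 28/25 = 26.88 h.
- Peak pain: the unrated migraine day drops out, because at least one other migraine day in the month has an NRS value.

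**3. Effect on the treatment comparison.** Let m be the share of attacks left unrecorded and μ the mean hours per attack. If missingness is unrelated to duration, the scored mean is about (1 − m) × μ. With equal baseline shares:

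shift in the difference (erenumab − placebo) ≈ −(m_erenumab − m_placebo) × μ

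The documents give neither m nor μ, so every row below rests on assumed values. A 5-point gap is, for example, 3% in one arm and 8% in the other.

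| μ (h) | Gap in m | Shift (h) | Share of 2.0 h | Rejection with no true effect | Power if the shift runs against erenumab |
|---|---|---|---|---|---|
| 8 | 2 points | 0.16 | 8% | 5.6% | 74.5% |
| 8 | 5 points | 0.40 | 20% | 8.8% | 62% |
| 12 | 5 points | 0.60 | 30% | 14% | 51% |
| 8 | 10 points | 0.80 | 40% | 21% | 40% |

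With shift b, rejection = 1 − Φ(1.96 − b/0.703) + Φ(−1.96 − b/0.703), and power = Φ((2.0 − b)/0.703 − 1.96). The arm that records less looks better.

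**4. Equal shares in both arms.** The true difference becomes 2.0 × (1 − m), which is 1.9 h at m = 5%. With the SD held at 8, power is 77% at m = 5%, 73% at 10% and 62% at 20%. If the SD shrinks in proportion, power is unchanged.

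**The case against.** The strongest reply is that the case may be rare. An ongoing headache is rated in each evening diary. SAP 5.1.1 also describes pain since the last entry being reported in the any-time diary or the next evening diary. One missed evening therefore need not leave an attack unrated. Headaches recurring within 48 hours merge into one attack, so one rated component supplies some hours. The documents do not say whether the eDiary forces entry of severity and duration, or how a headache with no end time is treated. The trial is blinded, and nothing in the documents predicts a gap between arms. All of this stands. It limits the likely size, but does not change what the rule does when the case occurs.

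Three stronger readings are tempting, and the documents do not support them:

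- **That this is the only endpoint with the problem.** The oral-triptan-treated average has the same form. Peak pain goes to 0 when no migraine day in the month has an NRS value. The primary counts a day with a rating but no duration as a day with no hours.
- **That recording must worsen after randomization, because criterion 111 requires 80% diary compliance at baseline and 14 of 28 days suffice later.** Those figures concern diary days. An attack on a missed day with no entry at all is absent from both numerator and denominator, so compliance does not measure unrated attacks.
- **That equal shares in both arms still produce a false finding.** They can distort the change within an arm, but the test compares erenumab with placebo, where the effect is mainly slight attenuation.

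**Conclusion.** The concern holds as a defect in a stated rule. In the average attack duration and its oral-triptan-treated version, a headache attack with unrecorded severity or duration is scored 0 h. The primary drops non-diary days without a rating, and peak pain drops individual unrated migraine days, though neither is free of missing-as-zero cases.

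The size is unknown. A shift of 0.4 to 0.6 h rests on an assumed mean of 8 to 12 h, an assumed 5-point gap between arms, equal shares at baseline, and missingness unrelated to duration. It shows that a modest gap would matter beside a standard error of 0.70 h; it is not a forecast. The planned power of 81% is correct under its own assumptions. The change is worth making because the endpoint is confirmatory, no sensitivity analysis is planned, and the correction is small.

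**What to change.** Before unblinding, amend SAP 5.1.1 so that the denominator counts evaluable attacks:

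- headache attacks with a recorded severity and, if that is moderate or severe, a recorded duration;
- mild-only attacks, at 0 h;
- treated aura-only events with no headache, at 0 h.

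Exclude headache attacks with unrecorded severity or duration. Set the month to missing if it has attacks but none is evaluable. Apply the same rule to the oral-triptan-treated average, and tabulate excluded attacks by arm.

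The aura clause is needed. A treated aura counts as an attack but need have no severity report, so requiring a report for every attack would delete true zeros.

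The cost is a short addition to the SAP and one flag in the derivation. Monthly averages will rest on slightly fewer attacks, and multi-day attacks recorded only in part will remain undercounted. Exclusion also treats a patient's recorded attacks as representative of the unrecorded ones, which is why the tabulation by arm should accompany it.

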Migraine recurrence	return of any headache of at least moderate pain intensity in patients who were pain-free at 2 hours post-dose
MMD	monthly migraine days
MSSS	Migraine Symptom Severity Score
NCT	National Clinical Trials
NRS	Numeric Rating Scale
pain relief	reduction from moderate/severe pain to mild/no pain
PCS	Pain Catastrophizing Scale
PFS	prefilled syringes
PGI-S	Patient Global Impression of Severity
PHQ-9	Patient Health Questionnaire
Q4W	every 4 weeks
QM	once monthly
Qualifying oral triptan-treated attacks (run-in period/month 4)	migraine attacks of at least moderate peak pain intensity that are treated with an oral triptan within 2 hours of pain reaching at least moderate severity
Qualifying oral triptan-treated attacks (baseline/ month 1, 2, and 3)	migraine attacks that are treated with an oral triptan
Randomization	defined as the day a subject has met all run-in and baseline period eligibility criteria and is enrolled and randomized into the study (subjects are enrolled same day)
SAP	statistical analysis plan
SC	subcutaneous(ly)

Abbreviation or Term	Definition/Explanation
Source d ata	information from an original record or certified copy of the original record containing patient information for use in clinical research. The information may include, but is not limited to, clinical findings, observations, or other activities in a clinical trial necessary for the reconstruction and evaluation of the trial. Source data are contained in source documents (original records or certified copies). (ICH Guideline [E6]). Examples of source data include Subject identification, Randomization identification, and Stratification Value.
Study d ay 1	defined as the first day that protocol-specified investigational product(s)/protocol-required therapies is/are administered to the subject
Total migraine freedom days	Days where there is an absence of headache and aura, photophobia, phonophobia, and nausea/vomiting
US	United States

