5.6 Arithmetic Calculations

Duration of Migraine

The number of years from the diagnosis date (DXDT) of migraine (migraine with aura or migraine without aura, whichever is earlier) to the date informed consent is signed.

Observed Portion	Missing Portion	Duration of Migraine (Years)
Year, Month, Day	NA	(Informed Consent Date – DXDT) / 365.25
Year, Month	Day	[Year(Informed Consent Date) – Year(DXDT)] + [Month(Informed Consent Date) – Month(DXDT)] / 12 ª
Year	Month, Day	[Year(Informed Consent Date) – Year(DXDT)] ^a

^a If it equals 0, add 1/12 years (ie, 1 month) to avoid a disease duration of 0.

Duration of IP Exposure

Minimum (Last Dose Date + 27, EOS Date) - First Dose Date + 1

Change From Baseline in Monthly Measurement

Postbaseline monthly value – Baseline, as defined in Section 5.4. If the baseline or postbaseline value is missing, the change from baseline value will be set to missing.

Change From Baseline in Mean Monthly Measurement Over Multiple Months

Change from baseline in Mean Monthly Measurement is the arithmetic mean of the monthly change from baseline values for the months considered with observed data, if there is at least one observed monthly value.

Subject Incidence of TEAEs

The subject incidence for a given event during the study is defined as the number of subjects with at least one reported occurrence of the event divided by the number of subjects who received at least one dose of investigational product. For subjects with multiple occurrences of the same event, the event will only be counted once per subject.

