Change from baseline in pain catastrophizing as measured by the Pain Catastrophizing Scale (PCS) at month 3 ^b	 Summary statistics using observed data at week 12 Analysis of covariance (ANCOVA) model including treatment group and baseline value using observed data Estimate treatment difference (AMG 334 – Placebo) using the model in #2.
Achievement of no or mild interictal burden as measured by the MIBS-4 at assessment time points ^c	 Summary statistics using observed data at the specific month Logistic regression model including treatment group and baseline value will be used after subjects with missing outcome data are imputed as non-responders (NRI)

Table 9-3. Exploratory Efficacy Endpoint Summary Table

Endpoint	Primary Summary and Analysis Method	
Achievement of pain freedom at 2 hours post-triptan dose for the first attack at month 4 ^d	Summary sta assessment f	itistics using observed data at the time points
	group will be	ession model including treatment used after subjects with missing ment are imputed as non-responders
Use of migraine rescue medication within 24 hours post-triptan dose for the first attack at month 4	Summary sta assessment	atistics using observed data at the time points
		ression model including treatment observed data
^a The same analyses methods will be applie	the endpoints:	

The same analyses methods will be applied to the endpoints:

Change from baseline in mean monthly hours of at least moderate pain intensity for qualifying oral triptan-treated migraine attacks over months 1, 2, and 3

Change from baseline in mean average duration of at least moderate pain intensity for qualifying oral triptan-treated migraine attacks occurring over months 1, 2, and 3

Change from baseline in Migraine Symptom Severity Score (MSSS) total score at assessment time points Change from baseline in mean monthly total migraine freedom days over months 1, 2, and 3

Change from baseline in Migraine Interictal Burden Scale (MIBS-4) total score at assessment time points (the model will include data at month 1-4)

Change from baseline in headache impact scores as measured by the Headache Impact Test (HIT-6) total score at assessment time points

Change from baseline in physical function domain score as measured by MFIQ at assessment time points Change from baseline in usual activities domain score as measured by MFIQ at assessment time points

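### The average-duration endpoint for oral triptan-treated attacks has no value for a month with migraine but no triptan-treated attack, because its zero rule tests for no migraine

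*SAP*

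**What the plan says.** SAP 5.1.1 takes the time in at least moderate pain "within a qualifying oral triptan-treated attack divided by number of qualifying oral triptan-treated attacks in each month". Two special cases follow. With fewer than 14 diary days the month is missing. Otherwise: "If there is no migraine during the monthly interval, then the monthly average duration will be set to 0". The same sentence serves the all-attacks average-duration endpoint defined just before it.

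The denominator here is a subset of migraine attacks. For baseline and months 1 to 3, Protocol 11.1 defines qualifying attacks as "migraine attacks that are treated with an oral triptan"; SAP 5.1.1 similarly requires a triptan taken between the start and end of the attack.

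Two neighbouring definitions in SAP 5.1.1 are useful for comparison. The companion monthly-hours endpoint is a prorated total, "Sum of hours of at least moderate pain intensity of qualifying oral triptan treated migraine attacks", and needs no zero rule. The peak-intensity endpoint scores 0 under the condition "If there is no migraine day with NRS during the monthly interval", which is the condition that empties its own denominator.

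SAP 5.6 states: "If the baseline or postbaseline value is missing, the change from baseline value will be set to missing". It then averages over the months with observed data. Footnote a of SAP Table 9-3 lists "Change from baseline in mean average duration of at least moderate pain intensity for qualifying oral triptan-treated migraine attacks" among the endpoints analysed by the linear mixed model. SAP 9.5.2 applies that model without imputation and plans no sensitivity analysis for exploratory endpoints.

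**The concern.** No migraine implies no triptan-treated attack, but the reverse does not hold. The zero rule fits the all-attacks endpoint, where having no migraine attack is exactly what makes the denominator zero. Used for the triptan-treated endpoint, it leaves out months in which the subject had migraine and took no triptan.

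Two kinds of month carry the same information about triptan-treated attacks, namely none. One scores 0, the lowest possible value; the other has no defined value. Attack frequency and the need for a triptan may both respond to treatment, so the share of each kind of month could differ between arms. The estimated difference would then depend partly on a coding decision that the SAP does not state, and two competent programmers could obtain different results from the same text.

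**Working it through.** The plan states no power, sample size or frequency for this endpoint, so there is no figure to reproduce. The check applies the rule literally, then sizes it under stated assumptions.

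**1. The rule applied to each kind of month with at least 14 diary days**

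| Month | Average duration, as written | Companion hours endpoint |
|---|---|---|
| (a) At least 1 triptan-treated attack | hours / attacks | prorated sum of hours |
| (b) Migraine, no triptan-treated attack | 0/0, no rule | 0 |
| (c) No migraine | 0 | 0 |

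The missing-data rules in SAP 5.6 and 8.3 and the methods in SAP 9.5 to 9.5.2 give no value for (b). An undefined value has no change from baseline, so under an observed-data model it is not used.

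**2. How often (b) and (c) might occur**

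Assume a Poisson number of migraine attacks with mean L per month on treatment, each independently triptan-treated with probability p. Neither L nor p is in the documents. Inclusion criterion 107 asks only that subjects typically start acute treatment with an oral triptan in more than 50% of attacks of at least moderate intensity.

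- P(c) = exp(-L)
- P(b) = exp(-Lp) - exp(-L)

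| L | P(c) | P(b), p = 0.5 | p = 0.6 | p = 0.7 | p = 0.8 |
|---|---|---|---|---|---|
| 3 | 5.0% | 17.3% | 11.6% | 7.3% | 4.1% |
| 4 | 1.8% | 11.7% | 7.2% | 4.2% | 2.2% |
| 5 | 0.7% | 7.5% | 4.3% | 2.4% | 1.2% |

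Example: L = 4, p = 0.6 gives exp(-2.4) - exp(-4) = 0.0907 - 0.0183 = 7.2%. P(b) exceeds P(c) only when L(1 - p) > ln 2 = 0.693. At L = 3, p = 0.8, L(1 - p) = 0.6 and the order reverses: 4.1% undefined against 5.0% migraine-free.

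**3. One subject (assumed data)**

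Baseline is 10 h. Month 1 has 3 triptan-treated attacks totalling 24 h, so 8 h. Month 2 is type (b), month 3 type (c).

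- As written: changes -2, undefined, -10; mean = -12/2 = -6.0 h
- 0 in both (b) and (c): -2, -10, -10; mean = -22/3 = -7.33 h
- Missing in both: -2 only; mean = -2.0 h

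**4. Two arms (assumed data)**

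Let each triptan-treated attack last 8 h in both arms, so there is no per-attack effect. Take (c) months at 10% versus 3% and (b) months at 10% versus 5% (erenumab versus placebo), leaving (a) months at 80% versus 92%. Simple arm means of monthly values are used, without the mixed model.

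- As written: 8 × 0.80/0.90 - 8 × 0.92/0.95 = 7.11 - 7.75 = -0.64 h
- 0 in both: 8 × 0.80 - 8 × 0.92 = 6.40 - 7.36 = -0.96 h
- Only months of type (a): 8 - 8 = 0 h

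Over four assumed sets of shares, the rule as written gave -0.05 to -0.69 h, and 0 in both gave -0.24 to -1.36 h. These figures show that the result depends on the coding; they do not predict this trial.

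**The case against.** **The SAP never says these months are missing.** Correct. It assigns missing only for fewer than 14 diary days. Because the rule sits in the definition for triptan-treated attacks, a programmer could take no migraine to mean no such migraine and code 0. A reader might infer that the plan deliberately sets the two kinds of month apart. The text does not support that: missing is only the literal consequence of 0/0 under an observed-data model. The ambiguity is itself the defect.

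**Subjects are not dropped.** A reader might infer that someone whose attacks no longer need a triptan leaves the analysis. What is lost is a subject-month. SAP 5.6 averages the remaining months, and the mixed model adjusts for baseline and, with a within-subject covariance structure, uses the subject's other months. Baseline is less exposed, because criteria 110 and 112 require at least 4 attacks of at least moderate severity and treatment of qualifying attacks with the same oral triptan as in the run-in.

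**The uncovered month need not be the commoner one.** This stands. The order reverses at L = 3, p = 0.8. The more-than-50% in criterion 107 is a floor and concerns starting treatment with a triptan, whereas the endpoint counts any triptan taken during the attack, which pushes p up. Untreated mild attacks push it down.

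**No bias is demonstrated.** This also stands. The arm-level hours rest on assumed durations and imbalances, and no arm difference in these months can be derived from the documents.

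**Scoring migraine-free months as 0 is the sponsor's convention.** It is also used for the parent secondary endpoint (footnote a of SAP Table 3-1). Setting those months to missing would override it and remove more months selected after randomization: exp(-Lp), or 9.1% instead of 7.2% at L = 4, p = 0.6. Choosing 0 or missing is an estimand decision. That argues for restraint in the repair, not for leaving the gap.

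**Conclusion.** The point holds as a minor error in a stated rule: the zero condition does not match the endpoint's denominator, and a month with migraine but no triptan-treated attack has no assigned value. This is more than missing detail, since the peak-intensity rule in the same section is keyed correctly and the companion hours endpoint treats both kinds of month alike.

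Under the assumed Poisson model, with 3 to 5 attacks per month and 50% to 80% triptan-treated, roughly 1% to 17% of months would be undefined and 0.7% to 5% migraine-free. The effect on the treatment difference cannot be sized from the documents.

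The endpoint is exploratory and outside the sequential testing procedure in SAP 9.1. A reader might infer that the secondary average-duration endpoint shares the defect; it does not, because there the zero rule matches the denominator. No primary or secondary test and no power figure changes.

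**What to change.** In SAP 5.1.1, key the rule to the endpoint's own denominator, for example: *In a month with at least 14 diary days and no qualifying oral triptan-treated migraine attack, the value is 0.* This keeps the SAP's existing zero convention and agrees with the companion hours endpoint. If the sponsor prefers missing as its estimand, both kinds of month should still be handled the same way.

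Tabulate by arm and month the number of months with migraine but no triptan-treated attack, and the number with no migraine. Under the 0 rule the arm difference also reflects how often such months occur. A supplementary version restricted to months with at least one triptan-treated attack, mirroring the conditional all-attacks endpoint, may therefore be added; it would carry the usual caution about selection after randomization.

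The cost is one sentence, one programming condition and one small table, with no new data, settled before unblinding. The optional supplement would be one further model run.
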